8.3. Serious Adverse Events

8.3.1. Definitions

A SAE is defined as an event that meets 1 of the following criteria:

- Is fatal or life-threatening (ie, immediate risk of dying).
- Results in persistent or significant disability or incapacity.
- Constitutes a congenital anomaly or birth defect.
- Is clinically meaningful (ie, defined as an event that jeopardizes the subject or requires potential medical or surgical intervention to prevent 1 of the outcomes listed above). Considered meaningful by the investigator as an important medical event that may not result in death, be life-threatening, or require hospitalization, but may be considered a SAE when, based upon appropriate medical judgment, it may jeopardize the subject or may require medical or surgical intervention to prevent 1 of the outcomes listed in this definition.
- Requires inpatient hospitalization or prolongation of existing hospitalization, unless hospitalization is a result of:
 - Routine treatment or monitoring of the studied indication not associated with any deterioration in condition. Elective or preplanned treatment for a pre-existing condition that is unrelated to the indication under study and has not worsened since signing the ICF.
 - Treatment on an emergency outpatient basis for an event not fulfilling any of the definitions of a SAE given above and not resulting in hospital admission.
 - Social reasons and respite care, in the absence of any deterioration in the subject's general condition.
 - Any SAEs that are expected due to the condition being treated, including if the SAE is a primary outcome measure, or where there has been a clear agreement with regulators not to consider these as SAEs, provided the information is collected elsewhere.

8.3.2. Reporting

To ensure subject safety, every SAE, regardless of suspected causality, occurring after the subject has signed the ICF and up to the last study visit, or up to 90 days after the last dose of study treatment, must be reported to the sponsor (or designee) within 24 hours of learning of its occurrence. Any SAEs experienced after this period should be reported to the sponsor (or designee) only if the investigator suspects a causal relationship to the study drug. Recurrent episodes, complications, or progression of the initial SAE must be reported as the follow-up to the original episode within 24 hours of the investigator receiving the follow-up information. An SAE occurring at a different time interval or otherwise considered completely unrelated to a previously reported one should be reported separately as a new event. Previously planned (before providing informed consent) surgeries should not be reported as SAEs unless the underlying medical condition worsens over the course of the study.

Information about all SAEs is collected and recorded on the Serious Adverse Event Report Form. The investigator must assess and record the relationship of each SAE to each specific study drug (if there is more than 1), complete the SAE Report Form in English, and send the completed, signed form by fax within 24 hours to the sponsor or its designee. The investigator must assess if there is a reasonable possibility that the SAE is related to the study treatment: unrelated (no) or related (yes).

Serious AEs related to unblinded comparator drugs or concomitant medications/drug delivery systems are reported directly to the manufacturers of those drugs/devices in accordance with the package insert.

The telephone and facsimile number of the sponsor's contact persons, specific to the study, are listed in the investigator folder provided to each site. The original copy of the SAE Report Form and the fax confirmation sheet must be kept with the CRF documentation at the study site.

Follow-up information is sent to the same person to whom the original SAE Report Form was sent, using a new SAE Report Form stating that this is a follow-up to the previously reported SAE and giving the date of the original report. Each recurrence, complication, or progression of the original event should be reported as a follow-up to that event regardless of when it occurs. The follow-up information should describe whether the event has resolved or continues, if and how it was treated, and whether the subject continued or withdrew from study participation, or if study drug was interrupted or discontinued.

If the SAE is not previously documented in the IBs for the study drugs (new occurrence) and is thought to be related to the sponsor's study drug, a sponsor's associate may urgently require further information from the investigator for reporting to health authorities.

The sponsor or its designee may need to issue an IN to inform all investigators involved in any study with the same drug that this SAE has been reported. Suspected Unexpected Serious Adverse Reactions will be collected and reported to the competent authorities and relevant ethics committees in accordance with Directive 2001/20/EC, or as per national regulatory requirements in participating countries.

8.3.2.1. Hepatic Function Abnormalities (Hepatotoxicity)

As defined in Section 8.2.2, Hy's law cases must be reported as SAEs. Additional information regarding hepatic function abnormalities is provided in Section 8.8.

8.4. Emergency Unblinding of Treatment Assignment

Not applicable.

8.5. Pregnancy

Pregnancy, in and of itself, is not regarded as an AE unless there is suspicion that study drug may have interfered with the effectiveness of a contraceptive medication or method. When a pregnancy has been confirmed, the following procedures should occur:

- The investigator must notify the sponsor or its designee immediately.
- The study drug must be discontinued immediately.
- The subject must be withdrawn from the study.
- The EOT visit evaluations must be performed.
- The investigator must complete and submit the Pregnancy Initial and Follow-Up Report forms to the sponsor or its designee.
- A serum pregnancy test must be performed to confirm the urine pregnancy test result. (The serum test should be performed at the investigative site to ensure the test will be performed promptly and the result available immediately for review.)

If a negative serum test does not confirm the urine pregnancy test result, then:

- The investigator will use his or her expert judgment, based on an assessment of the potential benefit/risk to the subject, to determine if it is in the subject's best interest to resume study drug and continue participation in the study.

To ensure subject safety, each pregnancy in a subject during maternal or paternal exposures to study drug must be reported within 24 hours of learning of its occurrence.

Data on fetal outcome and breastfeeding are collected for regulatory reporting and drug safety evaluation. Follow-up to each pregnancy should be conducted to determine outcome, including spontaneous or voluntary termination, details of the birth, and the presence or absence of any birth defects, congenital abnormalities, or maternal and/or newborn complications, by following until the first well-baby visit. Pregnancy should be recorded on a Clinical Study Pregnancy Form and reported by the investigator to the sponsor or its designee. Pregnancy follow-up should be recorded on the same form and should include an assessment of the possible relationship to the sponsor's study drug of any pregnancy outcome and follow-up to the first well-baby visit. **Any SAE experienced during pregnancy must be reported on the SAE Report Form and to the sponsor or its designee.**

8.6. Warnings and Precautions

No evidence available at the time of the approval of this study Protocol indicated that special warnings or precautions were appropriate, other than those noted in the provided IBs. Additional safety information collected between IB updates will be communicated in the form of INs. Any important new safety information should be discussed with the subject during the study as needed. If new, significant risks are identified, they will be added to the ICF.

8.7. Data Monitoring Committee

There will be no formal external Data Monitoring Committee for this open-label study. Approximately weekly the sponsor will conduct telephone conferences with investigators in order to review cohort-specific data, overall safety data from prior cohorts (if applicable), and to agree on dose escalation, de-escalation, and cohort expansion decisions.

8.8. Adverse Events of Special Interest

Adverse events of special interest include irAEs that are seen with immunotherapy and any other observed autoimmune phenomenon. Guidance for the assessment, diagnosis, and management of irAEs is provided in Section 5.6.3. Immune-related AEs will be monitored carefully at each cycle and during the safety follow-up period.

Adverse events of special interest for durvalumab are events of scientific and medical interest specific to the further understanding of the durvalumab safety profile and require close monitoring and rapid communication by the investigator to the sponsor. Durvalumab AEs of special interest may be serious or nonserious. The rapid reporting of these AEs of special interest allows ongoing analysis of these events in order to characterize and understand them in association with the use of this investigational product. Durvalumab, an anti-PD-L1 antibody, binds with high affinity and specificity to PD-L1 and blocks its binding to PD-1 and CD80, thus promoting antitumor immunity and tumor cell killing. Potential risks based on this mechanism of action of durvalumab and related molecules include immune-mediated reactions such as enterocolitis, dermatitis, hepatotoxicity or hepatitis, endocrinopathy, neuropathy, and pneumonitis. The class including anti-PD-L1 drugs and other immune checkpoint antibodies such as anti-PD-1 or anti-CTLA-4, have a wide spectrum of immune-mediated reactions that have been considered inflammatory in nature and can affect any organs of the body.

8.8.1. Pneumonitis

Pneumonitis has been reported in association with use of anti-PD-L1/anti-PD-1 antibodies (Brahmer et al 2012). Initial work-up should include a high-resolution CT scan, ruling out infection, and pulse oximetry. Pulmonary consultation is recommended. Guidelines for the management of subjects with immune-mediated events including pneumonitis are outlined in Section 5.6.3.1.

8.8.2. Hypersensitivity Reactions

Hypersensitivity reactions as well as infusion-related reactions have been reported with anti-PD-L1 and anti-PD-1 therapy (Brahmer et al 2012). As with the administration of any foreign protein and/or other biologic agents, reactions following the infusion of monoclonal antibodies can be caused by various mechanisms, including acute anaphylactic (IgE-mediated) and anaphylactoid reactions against the monoclonal antibody, and serum sickness. Acute allergic reactions may occur, may be severe, and may result in death. Acute allergic reactions may include hypotension, dyspnea, cyanosis, respiratory failure, urticaria, pruritus, angioedema, hypotonia, urticaria, arthralgia, bronchospasm, wheeze, cough, dizziness, fatigue, headache, hypertension, myalgia, vomiting, and unresponsiveness.

Guidelines for management of subjects with hypersensitivity (including anaphylactic reaction) and infusion-related reactions are outlined in Section 5.1.2.2.

8.8.3. Hepatic Function Abnormalities (Hepatotoxicity)

Increased transaminases have been reported during treatment with anti-PD-L1 (Brahmer et al 2012). Inflammatory hepatitis has been reported in 3% to 9% of subjects treated with anti-CTLA-4 monoclonal antibodies (eg, ipilimumab). The clinical manifestations of ipilimumab-treated subjects included general weakness, fatigue, nausea and/or mild fever, and increased liver chemistry tests such as AST, ALT, alkaline phosphatase, and/or total bilirubin. Hepatic function abnormality is defined as any increase in ALT or AST to $> 3 \times$ ULN and concurrent increase in bilirubin to $> 2 \times$ ULN (ie, Hy's law cases). Concurrent findings are those that derive from a single blood draw or from separate blood draws taken within 8 days of each other. Follow-up investigations and inquiries will be initiated promptly by the investigational site to determine whether the findings are reproducible and/or whether there is objective evidence that clearly supports causation by a disease (eg, cholelithiasis and bile duct obstruction with distended gallbladder) or an agent other than the investigational product. If the underlying diagnosis for the hepatic function abnormality is known (including progression of pre-existing disease such as primary or metastatic malignancy), the diagnosis should be recorded as an AE/SAE. If the underlying diagnosis for the hepatic function abnormality remains unknown, the term "hepatic function abnormal" should be used to report the AE/SAE. Hepatic function abnormality of unknown etiology, or which is considered attributable to investigational product, is required to be reported as "hepatic function abnormal" within 24 hours of knowledge of the event to the sponsor using the SAE Report Form, even if the event is considered to be nonserious.

The investigator will review the data with the medical monitor. The investigator should then use clinical judgment to establish the cause based on local standard of care and follow the subject by conducting testing as clinically indicated.

8.8.4. Serotonin Syndrome

As noted in Section 1.3.1, there is a theoretical chance that epacadostat could cause an increase in serotonin levels in the brain that might trigger SS (Boyer and Shannon 2005) when administered in combination with other serotonergic agents. This syndrome has been most closely associated with use of MAOIs, meperidine, linezolid, or methylene blue; all of these agents are prohibited during the study. Selective serotonin reuptake inhibitors and SNRIs are permitted in the study. Procedures listed in Section 5.6.4 will be implemented if subjects exhibit the signs/symptoms of SS, including tremor, hyperreflexia, and spontaneous ocular or inducible clonus together with agitation, fever, diaphoresis, or muscle rigidity.

8.9. Product Complaints

The sponsor collects product complaints on study drugs and drug delivery systems used in clinical studies in order to ensure the safety of study participants, monitor quality, and facilitate process and product improvements.

All product complaints associated with material packaged, labeled, and released by the sponsor or its designee will be reported.

The investigator or his/her designee is responsible for reporting a complete description of the product complaint and any associated AEs via email or other written communication to the Incyte contact.

If the investigator is asked to return the product for investigation, he/she will return a copy of the product complaint communication with the product.

9. STATISTICS

9.1. Study Populations

Safety Evaluable: All subjects enrolled who take at least 1 dose of study drug.

Pharmacokinetic [REDACTED] Evaluable: Includes subjects who received at least 1 dose of study drug(s) and provided at least 1 postdose blood sample for PK [REDACTED] [REDACTED] assessments [REDACTED]. The study pharmacokineticist will review data listings of subject dosing and sample records to identify subjects to be excluded from the analysis.

Phase 1 Population: All subjects enrolled in the Phase 1 portion of the study taking at least 1 dose of study drug.

9.2. Selection of Sample Size

9.2.1. Cohort Size in Phase 1

The primary objective of the open-label Phase 1 portion of the study is to determine the MTD or PAD and DLT of epacadostat in combination with durvalumab. The total number of subjects will depend on the number of dose levels tested before the MTD or PAD is established. Up to 36 subjects (6 subjects per dose level for 6 dose levels) will be included based on the dose escalation. Dose escalation will follow the 3 + 3 design algorithm as defined in Section 4.1.1. Based on this algorithm, which enrolls 3 evaluable subjects in each cohort with a maximum of 6 subjects at any dose level, the probabilities of dose de-escalation from a given dose level for the various DLT rates are provided in Table 32.

Table 32: Probability of Dose De-Escalation for Various DLT Rates

True DLT Rate	Probability of Dose De-Escalation
20%	23.6%
30%	47.2%
40%	68.3%
50%	83.4%
60%	92.4%

For example, if the true DLT rate is 50% at a given dose level, there is a 17% chance that the dose would be escalated. Further, if the true DLT rate is 20%, there is a 76% chance that the dose would be escalated.

9.2.2. Sample Size for Phase 2

The sample size for the melanoma, TNBC, and gastric and GE junction cohorts will be guided by the Simon 2-stage design (Simon 1989). Let P_0 denote a clinically uninteresting response rate (eg, for melanoma $P_0 = 30\%$). In order to determine whether a target response rate (eg, 55%) is likely, an initial number of subjects (eg, 15) will be treated at first in a cohort (Stage 1). For example, in a group in which ≤ 5 subjects have responses, it will be concluded that the true response rate is unlikely to be greater than or equal to the target rate and no more subjects will be enrolled in that group in Stage 2. Otherwise, in the groups in which at least 6 responses among the Stage 1 subjects is observed, 25 additional subjects will be treated in Stage 2 to estimate the response rate. At the end of Stage 2, if ≤ 16 subjects have responded among a total of 40 subjects, the drug will be declared nonpromising. In other words, after the study is finished, if there is a sufficient number of responses in the 2 stages combined, the study compound is considered promising; otherwise it is considered nonpromising. The detail is displayed in Table 33 using a Type I error of 0.05 and power of 90% for estimation.

Table 33: Details of Simon 2-Stage Design (Melanoma, TNBC, and Gastric and Gastroesophageal Junction Cancer)

	Melanoma ($P_0 = 30\%$, Target RR = 55%)	TNBC ($P_0 = 15\%$, Target RR = 40%)	Gastric and GE Junction ($P_0 = 10\%$, Target RR = 40%)
Drug is not promising if Stage 1 responder number \leq	5	2	1
Sample size for Stage 1	15	13	9
Drug is not promising if total responder number \leq	16	7	4
Sample size total	40	29	20

Under Amendment 6, enrollment of the NSCLC, SCCHN, and TCC of the GU tract cohorts will be completed as expansion cohorts at the 300 mg BID dose level. The sample size for each cohort will be increased to account for the heterogeneity of PD-1 pathway–treated and PD-1 pathway–naive subjects within the selected tumor types. The approximate number of subjects per tumor type is listed in Table 34, and the number of PD-1 pathway–treated subjects in each cohort will be limited to 10 in order to reduce the risk of any cohort having a significant imbalance between PD-1 pathway–treated and PD-1 pathway–naive subjects, thereby preserving the predicted levels of baseline efficacy observed with PD-1 pathway monotherapy. Subjects enrolled at the 100 mg BID will be analyzed independently. The sample size for each cohort expansion is based on a power of 90% to detect a target ORR of about 20% increase with a 1-sided alpha of 10% and 10% lost to follow-up.

Table 34: Sample Size Details (NSCLC, SCCHN, and TCC of the GU Tract)

Tumor Type	ORR		Sample Size
	H_0	H_a	
NSCLC	10%	30%	28
SCCHN	10%	30%	28
TCC of the GU Tract	10%	30%	28

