4.1.1. Phase 1 Dose Escalation

Phase 1 is the dose-escalation phase, which will include up to 6 cohorts of subjects treated with epacadostat at doses of 25 mg BID, 50 mg BID, 75 mg BID, 100 mg BID, and 300 mg BID in combination with durvalumab 3 mg/kg or 10 mg/kg given on Day 1 of each 14-day cycle. A minimum of 3 subjects will be enrolled and treated in each cohort, and all 3 subjects will be observed for a minimum of 42 days before the subsequent cohort begins enrollment.

Subjects must have received the cohort-specific dose of epacadostat for at least 75% of the doses (63 doses) and have received at least 3 doses of durvalumab during the 42-day DLT observation period, or have experienced a DLT to be evaluable for dose tolerability. Additional subjects will be enrolled in a cohort to achieve the minimum of 3 evaluable subjects if dropouts or dose interruptions/reductions occur that result in a subject being nonevaluable for DLTs.

The dose of epacadostat will be escalated if 0 of the first 3 evaluable subjects enrolled experience a DLT. If 1 of the first 3 evaluable subjects enrolled experience a DLT, the cohort will be expanded to include 3 additional evaluable subjects. If 2 or more of either 3 or 6 subjects enrolled experience a DLT, the prior dose level will be considered the MTD. If only 3 subjects were treated at this dose level, the dose will be confirmed as the MTD by evaluation of an additional 3 subjects before this dose is recommended for Phase 2 testing.

The cohorts and dose levels are shown in [Table 4](#).

Table 4: Dosing Cohorts

Cohort	Maximum Daily Dose of Epacadostat	Dose of Durvalumab (Once Every 14 Days)
1	25 mg BID orally	3 mg/kg IV
2	25 mg BID orally	10 mg/kg IV
3	50 mg BID orally	10 mg/kg IV
4	75 mg BID orally	10 mg/kg IV
5	100 mg BID orally	10 mg/kg IV
6	300 mg BID orally ^a	10 mg/kg IV

^a Intermediate dose levels may be explored based on emerging PK or pharmacodynamic data.

During the study, dose interruptions and/or dose decreases may be implemented based on toxicity as described in Section 5.6.

For the definition of DLT, see Section 5.5.1.

All subjects who received epacadostat and durvalumab in the dose-escalation phase and remain on study treatment will be observed for at least 42 days from the first dose prior to enrolling subjects in Phase 2 of the study.

4.1.2. Phase 2

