4.2. Study Endpoints

4.2.1. Primary Endpoints

- Phase 1: MTD or PAD. The MTD is defined by the highest dose cohort where no more than 1 of 6 subjects experience a DLT, or the highest Protocol-defined dose for each agent in the absence of exceeding the MTD. Alternatively, the PAD is defined as a tolerated dose of epacadostat (in combination with durvalumab) that produces substantial pharmacological target inhibition. Safety and tolerability will be assessed by monitoring the frequency, duration, and severity of AEs, through physical examinations, by evaluating changes in vital signs and ECGs, and through clinical laboratory blood and urine sample evaluations.
- Phase 2: Objective response rate determined by radiographic disease assessments per mRECIST v1.1 described in Sections 1.5.1 and 7.4.

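### The 3 + 3 de-escalation probabilities (Protocol Table 32, SAP Table 3) do not follow from the stated rule: at a 20% DLT rate the figure is 29.1%, not 23.6%

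*Protocol*

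**What the plan says.** Protocol 4.1.1 sets the rule in three steps. With no DLT in the first group of 3, the next dose level opens. A single DLT leads to a larger cohort: "If 1 of the first 3 evaluable subjects enrolled experience a DLT, the cohort will be expanded to include 3 additional evaluable subjects". Rejection is then judged on the running total at that level: "If 2 or more of either 3 or 6 subjects enrolled experience a DLT, the prior dose level will be considered the MTD".

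The primary endpoint definition in Protocol 4.2.1 fits this: "The MTD is defined by the highest dose cohort where no more than 1 of 6 subjects experience a DLT".

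Protocol 9.2.1 ties its table to the same rule: "Dose escalation will follow the 3 + 3 design algorithm as defined in Section 4.1.1". It describes the algorithm as one "which enrolls 3 evaluable subjects in each cohort with a maximum of 6 subjects at any dose level". Table 32 then gives de-escalation probabilities of 23.6%, 47.2%, 68.3%, 83.4% and 92.4% for true DLT rates of 20%, 30%, 40%, 50% and 60%. Two examples follow. One puts escalation at 17% when the true rate is 50%. The other reads: "Further, if the true DLT rate is 20%, there is a 76% chance that the dose would be escalated".

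SAP 3.1 states the same per-level rule. SAP 3.3.1 (Table 3) prints the same five values and the same two examples.

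**The concern.** The 20% row can be checked by hand and does not come out. Once 1 of the first 3 subjects has had a DLT, a single further DLT among the next 3 makes 2 of 6 and rejects the dose. The printed 23.6% is too low for that.

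Table 32 is the only operating characteristic the plan offers for the rule that determines the MTD, and Phase 2 is run at the MTD or PAD from Phase 1. A reader judging whether the rule is too cautious or too permissive has nothing else to go on. At 20% and 30% the table understates how often the rule turns a dose down. At 50% and 60% it slightly overstates this. The design therefore looks somewhat more discriminating than it is.

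**Working it through.** **Inputs.** First group of 3; 3 more added after 1 DLT in 3; rejection at 2 or more DLTs in 3 or in 6 (Protocol 4.1.1, SAP 3.1); at most 6 subjects per level (Protocol 9.2.1). Let p be the true DLT rate, X the DLTs among the first 3, and Y those among the subjects added. Subjects are taken as independent with the same p.

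**Step 1: reproduce the printed figures.** Of the variants tried, only this formula returns all five to the printed digit, with Y6 the DLTs among six *new* subjects:

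P(X ≥ 2) + P(X = 1) × P(Y6 ≥ 2)

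| p | P(X ≥ 2) | P(X = 1) | P(Y6 ≥ 2) | Result | Printed |
|---|---|---|---|---|---|
| 20% | 0.104 | 0.384 | 0.3446 | 23.6% | 23.6% |
| 30% | 0.216 | 0.441 | 0.5798 | 47.2% | 47.2% |
| 40% | 0.352 | 0.432 | 0.7667 | 68.3% | 68.3% |
| 50% | 0.500 | 0.375 | 0.8906 | 83.4% | 83.4% |
| 60% | 0.648 | 0.288 | 0.9590 | 92.4% | 92.4% |

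This ignores the DLT already seen and implies 3 + 6 = 9 subjects at one level, against the stated cap of 6. The other variants fail on at least one row. Examples are a fixed 6 subjects with 2 or more DLTs (34.5% at p = 20%), 2 or more DLTs required in the second 3 (14.4%), and a fixed 5 subjects with 2 or more (26.3%).

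**Step 2: apply the stated rule.** After 1 of 3, rejection needs at least 1 DLT among the 3 subjects added:

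P(de-escalate) = P(X ≥ 2) + P(X = 1) × P(Y3 ≥ 1), where P(Y3 ≥ 1) = 1 − (1 − p)³

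| p | Calculation | Correct | Printed | Correct minus printed (points) |
|---|---|---|---|---|
| 20% | 0.104 + 0.384 × 0.488 | 29.1% | 23.6% | +5.5 |
| 30% | 0.216 + 0.441 × 0.657 | 50.6% | 47.2% | +3.4 |
| 40% | 0.352 + 0.432 × 0.784 | 69.1% | 68.3% | +0.8 |
| 50% | 0.500 + 0.375 × 0.875 | 82.8% | 83.4% | −0.6 |
| 60% | 0.648 + 0.288 × 0.936 | 91.8% | 92.4% | −0.6 |

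Simulating the stated rule with 200,000 replicates per rate gave 29.3%, 50.7%, 69.0%, 82.7% and 91.8%, in line with the exact values.

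**Step 3: the two examples.** At 20% the chance of escalation is 100 − 29.1 = 70.9%, so 76% should read 71%. At 50% it is 100 − 82.8 = 17.2%, so 17% stands.

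**The case against.** The arithmetic itself is not open to dispute. Both tables are intact and identical, and the worked examples agree with them. The fair objections concern weight and wording.

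- **Size.** Three of the five rows are within 1 point. At 40% the printed value is too low, not too high, so the overstatement at the toxic end is confined to 0.6 points at 50% and 60%. This stands: the material errors are the 20% and 30% rows.
- **Consequence.** The 36-subject ceiling is 6 subjects × 6 levels and does not use these probabilities. The Phase 2 dose may be a PAD instead of the MTD, and Protocol 5.5 and 5.5.1 bring in cumulative and lower-grade toxicity. This also stands: the 3 + 3 rule is one input, and the table is descriptive.
- **Timing.** The protocol is Amendment 7 (21 SEP 2018), and Phase 2 subjects had been enrolled before Amendment 5. A correction cannot change a Phase 1 decision; it corrects the record and whatever later repeats these figures.
- **Escalation after 1 of 6.** Protocol 4.1.1 writes out escalation only for 0 of 3. The 71% assumes that 1 of 6 also leads to escalation. That follows from the rejection rule and the MTD definition. The plan's own 76% makes the same assumption, being 100 − 23.6. The de-escalation column does not need it.
- **Source of the error.** The documents print no formula. The six-new-subjects explanation is inferred from its fit to all five values.

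Confirming an MTD with 3 further subjects does not rescue the table. That step can only raise the chance of rejection; judging all 6 outright gives 34.5% at p = 20%, further from 23.6%.

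**Conclusion.** The point holds. Both tables claim to describe the algorithm in Protocol 4.1.1 and do not. At a 20% DLT rate the rule rejects the dose in 29.1% of cases instead of 23.6%, so the printed value understates rejection by about a fifth (5.5 / 29.1). At 30% the correct value passes one half (50.6%): such a dose is slightly more likely to be rejected than escalated, where the table implies the reverse. From 40% to 60% the differences are under 1 point.

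The result assumes independent subjects with a common DLT rate at a level, full evaluability, and the rule applied as written. The SAP was written for Amendment 1 with seven dose levels, but its per-level rule is the same, so the same correction applies. The error lies in the stated performance of the design. It does not alter the escalation rule, the sample size or the analyses.

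**What to change.** In Protocol 9.2.1 (Table 32) and SAP 3.3.1 (Table 3), replace the de-escalation probabilities with 29.1%, 50.6%, 69.1%, 82.8% and 91.8%. In the example at a 20% DLT rate, change 76% to 71%; leave the 17% example as it is. A one-line note under each table should give the formula and say that 1 DLT in 6 is counted as escalation, so that the figures can be checked.

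The cost is five numbers and one sentence in each document, plus the note. Any later report that repeats the table should carry the corrected values.
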